2.1 Primary Objective

- To assess the safety of rovalpituzumab tesirine when administered in combination with nivolumab or nivolumab and ipilimumab in adult subjects with extensive-stage SCLC

2.2 Secondary Objective

- To explore the efficacy of rovalpituzumab tesirine when administered in combination with nivolumab or nivolumab and ipilimumab in adult subjects with extensive-stage SCLC

2.3 Exploratory Objectives

- To explore the expression of DLL3 and PD-L1 in SCLC and their relationship to clinical outcome during treatment
- To explore the pharmacokinetics (PK) of and incidence of anti-therapeutic antibodies (ATA) against rovalpituzumab tesirine, nivolumab, and ipilimumab
- To explore the effect of study drug regimen on disease and immune biomarkers

2.4 Endpoints

2.4.1 Safety Endpoints

Analyses of the safety endpoints will include the following measurements or assessments:

- Adverse Events (AEs) and Dose-Limiting Toxicities (DLTs)
- Vital signs (Section 7.7.2)
- Body weight (Section 7.7.2)
- Laboratory abnormalities (Sections 7.7.3 and 8.3.7)
- Electrocardiographic parameters (e.g. QT interval corrected for heart rate [QTc], QT interval corrected for heart rate by Fridericia's formula [QTcF]) (Section 7.7.4)
- Echocardiography (Section 7.7.5)
- Eastern Cooperative Oncology Group (ECOG) performance status (Section 7.7.6)
- Monitoring of concomitant medications

2.4.2 Efficacy Endpoints

- Response assessments per Response Evaluation Criteria in Solid Tumors (RECIST) v1.1, including ORR and CBR
- Duration of response (DOR)
- Progression-free survival (PFS)
- PFS status after 6 months from the initiation of study treatment
- OS

2.4.3 Radiographic imaging, Pharmacokinetics, Biomarker, and Pharmacodynamic Endpoints

Analyses of the endpoints will include the following assessments:

[figure not shown]
- Specific PK parameters of rovalpituzumab tesirine, nivolumab, and ipilimumab
- ATA incidence and timing
- Tumor DLL3 and PD-L1 expression
- XXXXXXXXXX
- Blood Soluble Markers
- Immune Markers
- Circulating Tumor Cells (CTCs)

3. Investigational Plan

3.1 Summary of Study Design

This is a multicenter study involving rovalpituzumab tesirine administered in combination with nivolumab or nivolumab and ipilimumab in subjects with SCLC. The study plans to include 3 cohorts of up to approximately 30 subjects each (Table 1). DLTs will be assessed during the DLT Evaluation Period (Section 3.1.1).

Figure 1. Study Schema

- * Up to 12 DLL3+ subjects will be enrolled into each cohort in order to obtain 6 evaluable subjects at the end of the 12 week DLT period.
- a. Based on the tolerability of the initial 6 DLL3+ subjects in cohort 1, enrollment may begin of up to 12 DLL3+ subjects into cohort 2. The same strategy will be used for cohort 3 enrollment. If a regimen appears intolerable, the dose of rovalpituzumab tesirine may be reduced to 0.2 mg/kg, or 0.1 mg/kg. Such changes will constitute a new cohort, and subsequent cohorts may then carry forward the tolerated dose.
- b. For each cohort, up to 30 total subjects may be enrolled as part of an expansion phase after evaluation of the tolerability of the first 6 evaluable subjects.

Table 1. Planned Cohorts in the Study

Cohort	Population	Rovalpituzumab tesirine	Nivolumab	Ipilimumab
1	2 nd line or later SCLC (Platinum-failure) (Section 4.1)	0.3 mg/kg q6wk x 2	360 mg q3wk beginning on Week 4 (Cycle 2) x 2 cycles, then 480 mg q4wk	–
2	2 nd line or later SCLC (Platinum-failure) (Section 4.1)	0.3 mg/kg q6wk x 2	1 mg/kg q3wk x 4 cycles beginning on Week 4 (Cycle 2), then 480 mg q4wk (monotherapy) after 6 week washout	1 mg/kg q3wk x 4 beginning on Week 4 (Cycle 2)
3	2 nd line or later SCLC (Platinum-failure) (Section 4.1)	0.3 mg/kg q6wk x 2	1 mg/kg q3wk x 4 cycles beginning on Week 4 (Cycle 2), then 480 mg q4wk (monotherapy) after 8 week washout	3 mg/kg q3wk x 4 beginning on Week 4 (Cycle 2)

Initially, up to 12 subjects will be enrolled into Cohort 1 in order to obtain 6 evaluable subjects through the DLT evaluation period of 12 weeks. If $\leq 1/6$ subjects being evaluated has a DLT, enrollment beyond 12 subjects may proceed (i.e., enrollment into Cohort 1 expansion may begin). Subjects who are considered DLT-inevaluable (e.g., due to withdrawal from study before completing the DLT evaluation period; see Section 3.1.1) will be replaced if required.

Based on the tolerability of the initial 6 evaluable subjects enrolled in Cohort 1, enrollment may begin of up to 12 subjects into Cohort 2. Once Cohort 2 is open, Cohort 1 may continue enrolling (up to 30 subjects total).

Up to 12 DLL3+ subjects may be enrolled into Cohort 2 initially in order to obtain 6 evaluable subjects through the DLT evaluation period of 12 weeks. This will continue for Cohort 3 as well.

Safety will be monitored throughout the trial by the safety monitoring committee (SMC) consisting at least of the medical monitor and biostatistician. After enrollment of up to 12 subjects in Cohort 1, the SMC will perform a safety review of the data. Based on the tolerability of the initial 6 evaluable subjects in Cohort 1, enrollment may begin of up to 12 subjects in Cohort 2. Once Cohort 2 opens, Cohort 1 may continue enrolling (up to 30 subjects total). Similarly, Cohort 3 may enroll up to 12 subjects upon review of the tolerability of the first 6 evaluable subjects in Cohort 2. Once Cohort 3 opens, Cohort 2 may continue enrolling (up to 30 subjects total). Based on the tolerability of the initial 6 subjects in Cohort 3, Cohort 3 may continue enrolling (up to 30 subjects total). The SMC may recommend further evaluation of the safety of a given combination or dose regimen, investigation of alternative dose regimens, a modification of the dosing interval, or a change in the maximum number of doses (or elimination) of any component of the regimen. In general, if a regimen

appears intolerable, the dose of rovalpituzumab tesirine may be reduced to dose level -1, 0.2 mg/kg, or level -2, 0.1 mg/kg. Such changes will constitute a new cohort, and subsequent cohorts may then carry forward the tolerated dose. For instance, if Cohort 1 is not tolerated, a new Cohort 4 consisting of rovalpituzumab tesirine 0.2 mg/kg and nivolumab 360 mg q3wk could be initiated; if tolerated, a new Cohort 5 consisting of rovalpituzumab tesirine 0.2 mg/kg, nivolumab 1 mg/kg and ipilimumab 1 mg/kg (nivolumab and ipilimumab doses from Cohort 2) could then be initiated. The SMC will also review cumulative safety data in order to identify safety concerns that may emerge due to cumulative exposure beyond the DLT window. The process for dose-escalation decisions and dose-interval recommendations, and the roles and responsibilities of the SMC may be detailed separately. The SMC will meet at a frequency defined in the SMC Charter.

Tumor response will be assessed according to the imaging schedule in Section 6.4.6. Treatment decisions by the investigator will be based on RECIST v1.1.

Subjects will be eligible to continue treatment until unacceptable toxicity, progressive disease (PD), withdrawal of consent, study termination, or completion of a planned course of treatment (if a regimen with a limited number of doses is selected), whichever occurs first. Subjects who discontinue study treatment prior to PD will be evaluated for response q6wk until 24 weeks, then q12wk until disease progression or initiation of new anticancer treatment, whichever occurs first, and will afterwards be followed for survival until death or study termination, whichever occurs first.

Blood samples for PK, immunogenicity, biomarker and PD assessments will be collected at protocol-defined time points to support the study endpoints (Sections 7.3 and 7.4).

3.1.1 Definition of Dose-Limiting Toxicities

The DLT evaluation period is the first 12 weeks of treatment for all subjects. DLTs are defined as any of the following in the DLT-evaluation period, graded according to the National Cancer Institute's Common Terminology Criteria for Adverse Events (NCI CTCAE), version 4.03 (see Appendix 13.6)

- Grade 4 thrombocytopenia (or Grade 3 thrombocytopenia with bleeding) lasting more than 7 days and/or requiring platelet transfusion
- Grade 4 neutropenia lasting more than 7 days, and/or requiring hematopoietic growth factor rescue, or any febrile neutropenia (Grade 3 or 4 neutropenia with concurrent fever $\geq 38.3^{\circ}\text{C}$)
- Grade 4 anemia unrelated to underlying disease

- Clinically-significant Grade 3 or 4 non-hematologic laboratory abnormality that does not resolve to Grade 0/1 or baseline within 7 days
- Grade 3 or 4 non-laboratory AE with the exception of fatigue, asthenia, nausea, or other manageable constitutional symptom

The following events will not be considered DLTs:

- Any AE \geq Grade 3 clearly determined to be unrelated to study drug(s) (e.g., disease progression)
- \geq Grade 3 isolated alkaline phosphatase, amylase, or lipase laboratory abnormality of any duration
- \geq Grade 3 endocrinopathies controlled by hormone replacement
- Grade 3-4 electrolyte abnormalities

3.1.2 Retreatment

Retreatment with rovalpituzumab tesirine may be permitted, with medical monitor and sponsor approval, for subjects who tolerate all doses of rovalpituzumab tesirine, achieve clinical benefit as defined by SD or better during the period of receiving rovalpituzumab tesirine, and then experience disease progression at least 12 weeks after the most recent dose of rovalpituzumab tesirine. The retreatment dose level and regimen for each subject will be determined by the medical monitor, sponsor (or designee), and the site investigator, not to exceed the maximum tolerated dose (MTD).

Retreatment with nivolumab, or nivolumab and ipilimumab will not be permitted.

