3.2.3 Rationale for Selection of Doses

In a recent Phase 1 study with rovalpituzumab tesirine, the MTD was established at 0.4 mg/kg q3wk based on the incidence of Cycle 1 toxicities, while the recommended Phase 2 dose (RP2D) in SCLC was chosen as 0.3 mg/kg q6wk based on the toxicity and efficacy profile during multiple cycle dosing (AbbVie data on file).

In an ongoing Phase 1 study, nivolumab 3 mg/kg q2wk, and nivolumab 1 mg/kg + ipilimumab 3 mg/kg q3wk, were found to be tolerated in SCLC ([Antonia, 2015](#)). Since the toxicities of these therapies have been generally non-overlapping, the starting dose regimens in this study will therefore be rovalpituzumab tesirine 0.3 mg/kg q6wk + nivolumab 360 mg q3wk, rovalpituzumab tesirine 0.3 mg/kg q6wk + nivolumab 1 mg/kg q3wk + ipilimumab 1 mg/kg q3wk, and rovalpituzumab tesirine 0.3 mg/kg q6wk + nivolumab 1 mg/kg q3wk + ipilimumab 3 mg/kg q3wk. In all dose levels, nivolumab will be administered at 480 mg q4wk when used as a single agent or after 2 cycles at 360 mg in Cohort 1.

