6.1 Enrollment

Subjects who provide informed consent will be screened for eligibility. Once screening procedures have been completed, and for those subjects who meet all of the entry criteria, a Registration and Enrollment Form will be completed and submitted to the sponsor or designee to confirm eligibility. Approved subjects will then be enrolled into a treatment cohort. Refer to the Study Binder for the enrollment form, contact numbers, and other details of enrollment.

Safety assessments (Section 2.4.1) will include physical examinations, vital signs, body weight, ECOG performance status, AE assessments, laboratory tests (Section 7.7.3), ECGs, echocardiograms, Fluid Retention Questionnaire, concomitant medications, AEs, and concomitant therapies will be recorded from Day 1 (pre-dose) through the safety reporting period. At the same time, subjects will maintain a diary of daily weights. Any protocol-related AE should be recorded from the time of informed consent as well as any concomitant therapies given for treatment of the AE.

Study activities are listed by visit in this section and descriptions of all study assessments are presented in Section 7. A schedule of events is provided in Appendix 13.1.

Subjects undergoing retreatment as described in Section 3.1.2 will follow the same study schedule from Screening through EOT and LTFU.

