8.1.1 Definitions

8.1.1.1 Adverse Event

An AE is defined as any untoward medical occurrence in a patient or clinical investigation subject administered a pharmaceutical product and which does not necessarily have a causal relationship with this treatment. An AE can therefore be any unfavorable and unintended sign (including an abnormal laboratory finding), symptom, or disease temporally associated with the use of a medicinal (investigational) product, whether or not the event is considered causally related to the use of the product.

Such an event can result from use of the drug as stipulated in the protocol or labeling, as well as from accidental or intentional overdose, drug abuse, or drug withdrawal. Any worsening of a pre-existing condition or illness is considered an AE. Worsening in severity of a reported AE should be reported as a new AE. Laboratory abnormalities and changes in vital signs are

considered to be adverse events only if they result in discontinuation from the study, necessitate therapeutic medical intervention, and/or if the investigator considers them to be AEs.

An elective surgery/procedure scheduled to occur during a study will not be considered an AE if the surgery/procedure is being performed for a pre-existing condition and the surgery/procedure has been pre-planned prior to study entry. However, if the pre-existing condition deteriorates unexpectedly during the study (e.g., surgery performed earlier than planned), then the deterioration of the condition for which the elective surgery/procedure is being done will be considered an AE.

All protocol-related AEs must be collected from the signing of the study specific informed consent until study drug administration.

In addition, adverse events with onset or worsening reported by a subject from the time that the first dose of study drug is administered until 100 days have elapsed following discontinuation of study drug administration will be considered as treatment-emergent adverse events.

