10.3.4 Analysis of Efficacy Endpoints

ORR is defined as the proportion of subjects whose best overall response is either CR or PR according to RECIST v1.1. The number and percentage of responders along with the corresponding 95% confidence interval (CI) will be provided for each cohort.

CBR will be analyzed in a way similar to the analysis of the ORR (described above).

DOR will be summarized for responders (i.e., subjects with CR or PR only) by cohort. PFS and OS will be summarized by cohort. Median DOR, PFS, and OS will be obtained by using the Kaplan-Meier approach. The PFS rate at additional time points may also be evaluated (e.g., 26, 39, and 52 weeks). Details of the analysis of efficacy endpoints will be described in the Statistical Analysis Plan.

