10.3.5.1 Treatment-Emergent Adverse Events

TEAEs reported during the study will be coded using a MedDRA dictionary. Incidence of TEAEs will be summarized by cohort.

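### The TEAE and exposure summaries take in retreatment, a different and individually set regimen, and the response definitions do not say whether it is excluded

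*Combined protocol and SAP*

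**What the plan says.** Section 3.1.2 allows, with medical monitor and sponsor approval, a further course of rovalpituzumab tesirine for subjects who tolerate every dose, reach SD or better while receiving it, "and then experience disease progression at least 12 weeks after the most recent dose of rovalpituzumab tesirine". On the checkpoint inhibitors it states: "Retreatment with nivolumab, or nivolumab and ipilimumab will not be permitted". On dose: "The retreatment dose level and regimen for each subject will be determined by the medical monitor, sponsor (or designee), and the site investigator", with the MTD as ceiling. Section 6.1 adds: "Subjects undergoing retreatment as described in Section 3.1.2 will follow the same study schedule from Screening through EOT and LTFU". Section 6.3 does not list the CT among the screening items dropped for these subjects, although recent scans may replace it.

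The analysis text does not mention this phase:

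- Section 8.1.1.1 counts as treatment-emergent any event with onset or worsening "from the time that the first dose of study drug is administered until 100 days have elapsed following discontinuation of study drug administration".
- Section 10.3.5.1: "Incidence of TEAEs will be summarized by cohort". Section 10.3.3 likewise tabulates doses received by cohort.
- Section 10.3.4: "ORR is defined as the proportion of subjects whose best overall response is either CR or PR according to RECIST v1.1". It gives this by cohort with a 95% confidence interval and leaves further efficacy detail to a SAP. The supplied document contains no SAP text.

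Section 1.4 compares the lower 95% bound for ORR with 23%, as one factor in deciding whether to advance the programme.

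**The concern.** The primary objective is the safety of the combination. Retreatment comes after the combination has failed, does not restart nivolumab or ipilimumab, and has no common dose. Section 3.1 makes a changed rovalpituzumab tesirine regimen a new cohort when the change is made for tolerability, but a retreated subject is not separated in any way. Events and doses from the second course would therefore appear in tables that readers take to describe the first. The mixing is also selective, because only subjects who tolerated all doses and had at least SD can qualify.

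For response, the exposed case is a subject with SD on the combination, then PD, then a confirmed PR during retreatment. No rule says whether this subject is a responder, or which baseline applies after re-screening.

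**Working it through.** **1. Is retreatment a different regimen?** The first course is 0.3 mg/kg q6wk x 2 plus the checkpoint inhibitors. Retreatment is set per subject up to the MTD. The only MTD figure given for this drug is in Section 3.2.3: "the MTD was established at 0.4 mg/kg q3wk". If that is the ceiling meant, it corresponds to 2 x 0.4 = 0.8 mg/kg per six weeks, against 0.3 mg/kg in the first course.

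**2. Does it fall in the TEAE window?** Rovalpituzumab tesirine is a study drug. If discontinuation means the last study-drug dose of any course, the whole retreatment course is inside the window. If it means the end of the first course, there is still overlap. In Cohort 1, Day 1 of successive cycles falls on days 1, 22, 43, 64, 92, 120 and 148.

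- Last nivolumab on day 120: window open to 120 + 100 = day 220.
- Scan 3 to 7 days before day 148: days 141 to 145. PD there is 98 to 102 days after the day-43 dose, so it meets the 12-week condition.
- Retreatment could then begin with up to 220 - 141 = 79 days of the window left, less re-screening time.

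**3. Does it reach the DLT window?** No. That window is 84 days. The earliest qualifying PD is day 43 + 84 = 127 after two doses, or day 1 + 84 = 85 after one.

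**4. The plan's own figures.** 3 x 30 = 90 subjects reproduces. 14/61 = 22.95%, the combination ORR in Section 1.3, rounds to 23%, although the protocol does not name it as the source of the benchmark.

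**5. What can one reclassified responder do at n = 30?** It adds 1/30 = 3.3 points. No interval method is named, so three were checked (two-sided 95% lower bounds):

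| Method | Last count not above 23% | First count above 23% |
|---|---|---|
| Clopper-Pearson | 12/30: 22.7% | 13/30: 25.5% |
| Wald | 12/30: 22.5% | 13/30: 25.6% |
| Wilson | 11/30: 21.9% | 12/30: 24.6% |

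With the exact bound, if k first-course non-responders become responders only through retreatment, the chance of exceeding 23% when the true first-course ORR is 23% is P(X >= 13 - k), X ~ Bin(30, 0.23):

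| k (assumed) | 0 | 1 | 2 | 3 |
|---|---|---|---|---|
| Probability | 1.1% | 2.8% | 6.4% | 13.1% |

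**6. Safety, as illustration only.** Assume 3 to 6 of 30 retreated (10 to 20%). Apply the 14% rate of related Grade 3 or higher serosal effusions in Section 1.4 to the second course, with every event in a subject not already counted. This gives 3 x 0.14 = 0.42 to 6 x 0.14 = 0.84 extra subjects, or 1.4 to 2.8 points for that term.

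**7. CBR.** Section 10.3.4 does not define it. If it means SD or better, as clinical benefit does in Section 3.1.2, retreated subjects already qualify and the count would not change.

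**The case against.** A reader might infer that the plan counts retreatment responses in ORR. The documents do not support that. Section 10.3.4 ties ORR to RECIST v1.1, says nothing about when best response ends, and defers detail to a SAP that was not supplied. Section 3.1 ends response evaluation, for subjects who stop before PD, at progression or new anticancer treatment. A late PR would also need a 30% fall from the baseline sum after PD, confirmed by a repeat assessment. This limits the likelihood but leaves the gap: retreatment is never classed as new anticancer treatment, the full schedule restarts, and Section 7.2.1 fixes only the progression date for subjects treated beyond progression.

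The synopsis names dose regimen alongside cohort as a unit of analysis. That permits a separate presentation, but nothing assigns retreatment to a regimen of its own.

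The size may be small. Retreatment is discretionary, the 14% rate is applied to people selected for tolerating earlier doses, and the 23% comparison is only one factor. The 12-to-13 example does not flip under Wilson, where 12 already exceeds 23%; there the crossing is from 11 to 12. All of this stands, and the magnitudes above are therefore conditional.

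The strongest objection concerns the remedy. Cutting cohort TEAEs at the first retreatment dose would remove late combination toxicity that is still inside the 100-day window. This is right, and the overall table should stay.

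Two further inferences also fail. Cohort opening and expansion are not contaminated, because they rest on the 12-week DLT window. Nor is it settled that retreatment is always rovalpituzumab tesirine alone, because Section 7.2.1 allows nivolumab and/or ipilimumab to continue beyond PD.

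**Conclusion.** The safety part holds on the text: the TEAE window and the by-cohort TEAE and exposure summaries include retreatment, wholly or, on the narrower reading of discontinuation, in part. The response part is an unstated rule: the protocol does not exclude retreatment-phase assessments from ORR, CBR or DOR, and does not count them either. One such responder can carry the lower bound across 23% at n = 30, but only if the first-course count is one short of the threshold (12 by the exact or Wald method, 11 by Wilson). The safety effect is a few points per term at most under the assumed 3 to 6 retreated subjects. The true number is not given and could be lower. The point should be fixed because the rule costs little to write now, whereas a rule chosen after retreatment responses are known would be open to challenge.

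**What to change.** 1. Keep the overall by-cohort TEAE table and its 100-day window. In Sections 10.3.3 and 10.3.5.1 add an initial-course exposure and TEAE table that flags events with onset on or after the first retreatment dose. Summarize retreatment-phase exposure, TEAEs and responses separately.
2. In Section 10.3.4 define best overall response, and with it CBR and DOR, from assessments up to and including the first RECIST v1.1 PD of the initial course, against the original baseline.
3. Reconcile the passages on who can be retreated and with what. Section 4 requires retreated subjects to meet no exclusion criterion, yet exclusions 1b, 1c and 1f carry no retreatment exemption, whereas 1a and 10 do. Sections 3.1.2 and 7.2.1 leave open whether checkpoint inhibitors continued beyond PD may overlap retreatment.

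The cost is protocol or SAP wording and one extra set of tables, with no new visits or data. Attribution of late events in the overlap period stays uncertain; the flag shows them but cannot resolve their cause.
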